**Figure 1 Study Design**

Note: All visits include blood and urine sample collection as well as safety assessment.  
D = dosing day; R = randomization

Note: All visits include blood and urine sample collection as well as safety assessment, except for Visit 2, which includes only blood sample collection.

D = dosing day; R = randomization

Subjects who discontinue the treatment but not the study, should perform the EDV at the next scheduled visit and then go to the following scheduled visits exactly as subjects who are still on-treatment, for a total of 3 months.

The table below shows all procedures to be conducted at the scheduled visits.

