- g Blood samples for complement activation panel and coagulation parameters will be taken around Cmax and are to be collected pre-dose and 2 hours post-dose.
- h Samples to be obtained pre-dose on dosing days.
- i PK sampling to be performed at Visits 4 (D8), 6 (D29), 7 (D43), 8 (D57), 9 (D71), 10 (D85), 12 (D113) and 14 (D141) and final follow-up visit/EDV. Schedule of sampling for Visits 4 (D8), 6 (D29), 8 (D57) are shown below.
  - Visit 4 (Day 8; Loading dose): pre-dose
  - Visit 6 (Day 29; Dose 3): pre-dose
  - Visit 8 (Day 57; Final dose): pre-dose
- j ADA sampling to be performed at Visits 3 (D1), 4 (D8), 6 (D29), 8 (D57), 10 (D85), 12 (D113), and 14 (D141), and final follow-up visit/EDV. ADA samples to be collected pre-dose on all dosing days.
- k If, for any reason, the sample is not drawn pre-dose on Visit 3 (D1), it may be taken at any visit until the Final follow-up/EDV visit.
- l Visit 1 and visit 2 may be combined.

BMI = body mass index; CSP = clinical study protocol; D = day; ECG = electrocardiogram; EDV = early discontinuation visit; HbA1c = haemoglobin A1c; LDL-C = low-density lipoprotein cholesterol; PCSK9 = proprotein convertase subtilisin/kexin type 9; RTSM = Randomization and Trial Supply Management.

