**Table 2 Populations for Analysis**

Population/Analysis set	Description
All enrolled subjects	All participants who sign the ICF.
All randomized subjects	All participants who were randomized. Participants will be analysed according to the treatment to which they were randomized.
Full analysis set	All randomized participants who received at least one dose of IP, in accordance with the intention to treat principle. Participants will be included in the analysis according to the treatment to which they were randomized. This is the primary analysis set.
Safety analysis set	All participants randomly assigned to study treatment and who take at least 1 dose of study treatment and for whom any post-dose data are available. Participants will be analysed according to the treatment which they actually received. If a participant received study intervention from the wrong kit for only part of the treatment duration and then switched to another, the associated treatment group for that participant will be the treatment group that participant was randomized to.
ADA analysis set	All participants randomly assigned to study treatment and who take at least 1 dose of study treatment and had at least one ADA assessment available. Participants will be included in the analysis according to the treatment to which they were randomized.
PK analysis set	All participants in the full analysis set who have at least one PK sample post dose. A patient will be considered as having at least one PK sample post dose if he has at least one plasma concentration that is not below LLOQ after the first dose. Subjects will be analysed according to the treatment which they actually received. However, only samples taken on patients planned to receive active

	treatment are analysed. Thus, patients planned to receive placebo but who finally received active treatment will not have any result available.
--	---

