**Table 5 Study phases**

Study phase	Phase Window for Analysis (Days)
Pre-treatment	before first dose of study IP (day <1 a )
On-treatment	> day 1 b to the end of study date

a Includes all measurements collected before first dose of IP. If the measurement is collected on day 1 it cannot be determined if it was done before or after the first dose of IP (due to missing time and/or planned time point), then it will be considered as collected after first dose of IP.

b Includes all measurements collected on the day of first dose of IP, at the time of IP intake and after.

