### 3.3.3.5 ECG

ECG parameters includes the following:

- RR (msec)
- PR (msec)
- QRS (msec)
- QT (msec)
- QTcF (msec)
- HR (beats/min)
- Overall evaluation (normal, abnormal). If abnormal also reason and clinically significance is collected

For each participant, RR, PR, QRS and QT will be calculated as follow: the mean value of all measurements will be taken provided that at least 2 measurements are present (and at least 3 consecutive beats were analysable in each ECG) or else, the averaged value at the corresponding target time point will be set to missing. QTcF will be calculated as  $QTcF = QT * RR^{-1/3}$ , where the QT interval is in milliseconds and the RR interval is in seconds. Heart rate will be calculated, based on the RR interval as  $HR = 60 / RR$  interval, where the RR interval is in seconds. Calculation of derived parameters will be performed after averaging of QT and RR data. Results from these calculations will be reported in the eCRF together with the overall evaluation.

ECG parameters are assigned to analysis visits and study phases as described in section 3.1.2 and section 3.1.3 respectively. Evaluations with missing or partially missing dates cannot be imputed to any study phase and analysis visit.

ECG last observation on treatment is defined as last available value among those in the on-treatment analysis phase.

Change from baseline is defined as the post-baseline visit value minus the baseline value.

Additionally, ECG values will be classified as normal (if value is within normal reference range), low (if value is below the normal reference range), and high (if value is above the normal reference range) according to the below normal reference ranges:

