#### **4.2.5.4 Immunogenicity**

The analysis will be based on the ADA analysis set.

Immunogenicity parameters are described in section 3.3.2.5. Baseline and post-baseline definitions are detailed in section 3.1.2. Immunogenicity parameters tables and listings will be based on the ADA analysis set and presented for each treatment group.

ADA will be summarized as categorical variables with the number and percentages with a positive result at the specific visit. Immunogenicity titre will be summarized descriptively as a continuous variable, only for ADA positive tests, with median, interquartile range, minimum, and maximum, at each analysis visit.

ADA will also be summarized including the following:

- ADA positive at baseline and/or post-baseline (ADA prevalence)
- TE-ADA positive (ADA incidence)
- Treatment-induced ADA positive
- Treatment-boosted ADA positive
- TE-ADA negative
- Both baseline and post-baseline positive
- Only baseline positive
- ADA persistently positive
- ADA transiently positive
- TE-ADA positive with maximum titre > median of maximum titres

Post baseline coincide with the on-treatment phase as described in section 3.1.3.

Treatment-induced ADA positive is defined as ADA negative at baseline and post-baseline ADA positive

Treatment-boosted ADA positive is defined as ADA positive at baseline and boosted the pre-existing titre post-baseline ( $\geq 4$ -fold increase).

TE-ADA positive is defined as the sum of treatment-induced ADA positive and treatment-boosted ADA positive.

TE-ADA negative is defined as ADA positive but not fulfilling the definition of TE-ADA positive.

ADA persistently positive is defined as either ADA negative at baseline and ADA positive at  $\geq 2$  post-baseline assessments (with  $\geq 16$  weeks between first and last positive) either ADA positive at last post-baseline assessment.

ADA transiently positive is defined as ADA negative at baseline, having at least one post-baseline ADA positive assessment and not fulfilling the conditions of ADA persistently positive.

The median of maximum titres is calculated based on the maximum titre for each ADA positive subject within each treatment group (including both baseline and post-baseline measurements).

Missing ADA results are considered negative for the derivation of the above categories. The above categories will be calculated only for subjects in the ADA analysis set.

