- number and percentage of subjects with non-serious AEs occurring with a frequency > 5.0% in any treatment group for each SOC and PT. This table will be produced as a separate pdf output to meet clinical trial transparency requirements and not for inclusion in the CSR. It will be delivered at the same time as the CSR outputs.
- the number of subjects with injection site reactions by HLT and PT
- the number of subjects with bleedings by SMQ and PT

A list of key subject information for subjects with AEs with outcome of death, subjects with SAEs, and subjects with AEs leading to discontinuation of IP will be provided. The durations reported in these tables, will be derived only for fully completed dates as below:

- Time from first dose of IP to AE (in days) will be calculated as the AE start date minus date of first dose of IP +1.
- Time from first dose to death (in days) will be calculated as the date of death minus date of first dose of IP +1.
- The same approach will be used for deriving time from start of treatment to AE becoming serious or discontinuation.
- Time from last dose prior to AE start and last dose prior to death (in days) will be calculated as the date of death minus the date of last dose prior to AE/death +1.

All the AEs will also be listed for all subjects included in the safety analysis set. AEs among ADA positive and ADA negative subjects will also be listed. A subject is considered ADA

negative if collected samples are tested negative at all timepoints, including baseline and post-baseline. Regarding ADA positive categories in section 4.2.5.4 are included.

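### Counting missing ADA results as negative, in an analysis set that needs only one ADA sample at any time, misclassifies participants without a baseline or without any post-dose result

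*SAP*

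**What the plan says.** SAP 4.2.5.4 lists ten derived ADA categories and then gives one missing-data rule for all of them: "Missing ADA results are considered negative for the derivation of the above categories". The categories are computed in the ADA analysis set. SAP Table 2 defines this as randomised, dosed participants who "had at least one ADA assessment available", and does not say whether that assessment must fall before or after dosing.

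The definitions that matter here, all in SAP 4.2.5.4, are:

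- **Treatment-induced:** negative at baseline, positive afterwards.
- **Treatment-boosted:** positive at baseline, with at least a fourfold rise in titre.
- **TE-ADA positive:** induced plus boosted.
- **TE-ADA negative:** reserved for participants who are ADA positive but do not meet the TE-ADA definition. It does not mean that no ADA was found.
- **Persistently positive:** either negative at baseline with at least two post-baseline positives whose first and last are 16 weeks or more apart, or "either ADA positive at last post-baseline assessment".
- **Transiently positive:** negative at baseline, at least one post-baseline positive, and not persistent.

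On sampling, footnote j of SAP Table 1 starts "ADA sampling to be performed at Visits 3 (D1), 4 (D8), 6 (D29), 8 (D57" and goes on to Days 85, 113 and 141 and the final or early discontinuation visit (EDV). Day 1 is thus the only scheduled pre-dose sample. Under SAP Tables 3 and 5, a Day 1 sample that cannot be placed before or after the first dose is treated as post-dose.

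**The concern.** TE-ADA incidence compares status before and after dosing, so it can be judged only in a participant tested at both times. The SAP puts an assumed negative in place of whichever side is missing, and the analysis set does not screen such participants out. The result mixes tested and untested participants in one percentage, with errors that run in opposite directions depending on which side is missing.

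Development of ADA is a listed secondary endpoint. SAP 4.2.6.1 also summarises adverse events by ADA category, and SAP 4.2.5.4 plots drug concentration, PCSK9 and LDL-C by ADA status. The protocol (9.4.2.2) leaves the ADA analysis entirely to the SAP, so no other text corrects the rule. The primary LDL-C analysis is not affected.

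**Working it through.** The documents give no ADA rate, missing-sample rate or ADA precision target, so there is no figure of the plan's own to reproduce. The check has three parts.

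**1. Classification by pattern, applying SAP 4.2.5.4 as written**

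| Baseline | Post-baseline | Result under the SAP | Actually assessable? |
|---|---|---|---|
| Negative | None available | TE-ADA non-event, kept in denominator | No |
| Positive | None available | Only baseline positive, and TE-ADA negative | No; boosting never assessed |
| Missing | Positive | Treatment-induced, so TE-ADA positive | No; ADA may have pre-existed |
| Missing | All negative | TE-ADA non-event | No baseline to compare with |

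In the third row the total is wrong only if the ADA pre-existed and was not boosted. A boosted case is TE-ADA positive either way and merely moves from boosted to induced. The Day 1 timing rule sharpens this row: one positive Day 1 sample of undeterminable timing is counted as post-baseline, which leaves the baseline missing. The same sample then yields both an assumed negative baseline and a post-baseline positive.

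**2. Size**

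From the documents: about 108 randomised 1:1:1:1, so 108/4 = 27 per arm. Assumed: x = 8 TE-ADA positives in an arm, and m = 1, 2 or 3 participants with no post-baseline result. The SAP reports x/27; the rate among those tested is x/(27 − m).

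| m | SAP rule | Tested only | Shortfall (points) | If all m were positive |
|---|---|---|---|---|
| 1 | 8/27 = 29.6% | 8/26 = 30.8% | 1.1 | 9/27 = 33.3% |
| 2 | 8/27 = 29.6% | 8/25 = 32.0% | 2.4 | 10/27 = 37.0% |
| 3 | 8/27 = 29.6% | 8/24 = 33.3% | 3.7 | 11/27 = 40.7% |

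The relative shortfall is m/27: 3.7%, 7.4% and 11.1%. The shift depends on the assumed x. With x = 3 the rate goes from 11.1% to between 11.5% and 12.5%; with x = 13, from 48.1% to between 50.0% and 54.2%.

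In the other direction, each participant with a missing baseline and pre-existing, non-boosted ADA adds 1/27 = 3.7 points (8/27 = 29.6% becomes 9/27 = 33.3%). With 20 in the arm it adds 1/20 = 5.0 points.

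For scale, the exact (Clopper-Pearson) 95% interval for 8/27 is 13.8% to 50.2%.

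**3. Persistent or transient**

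Scheduled post-baseline ADA days are 8, 29, 57, 85, 113, 141 and 169, and 16 weeks is 112 days. Take a baseline-negative participant who is positive on Days 85, 113 and 141, with Day 169 missing. The span is 141 − 85 = 56 days, so the 16-week route fails and the class rests on the last assessment. If that means the last available result (Day 141), the participant is persistent. If the missing Day 169 result counts as a negative assessment, the participant is transient. By contrast, positives on Days 8 and 141 span 133 days and give persistent under either reading.

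**The case against.** The best defence is that the rule is explicit, its denominator is defined, and its triggers should be rare. To be untested after dosing, a participant must miss Day 8, every later scheduled sample and the EDV. A missing baseline should also be unusual, because the protocol (1.3 and the Visit 3 description in Section 8) requires assessments before dosing and a pre-dose ADA sample. The by-visit ADA summary lies outside the rule, and all immunogenicity data are listed, so untested participants can be traced. Counting a missing baseline as negative errs towards reporting more ADA, and an evaluable-only denominator makes its own assumption about the untested. All of this stands as argument about size. It does not make the classifications in the first and third rows of the table right.

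It is also fair that the last assessment most naturally means the last one made. The weakness there is an undefined term next to a rule that turns missing results into negatives.

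Three stronger readings are tempting, and the documents do not support them.

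- **That other SAP wording contradicts the rule.** SAP 4.2.6.1 calls a participant ADA "negative if collected samples are tested negative at all timepoints, including baseline and post-baseline", but this is a different label, used for adverse event listings. If only collected samples count, it gives the same positive or negative status as 4.2.5.4. It differs only if both a baseline and a post-baseline test are required. So the two are unreconciled, not clearly in conflict. Table 5 ("Includes all measurements collected on the day of first dose of IP, at the time of IP intake and after") allocates measurements to phases, and the ECG rule ("defined as last available value among those in the on-treatment analysis phase") concerns another variable. The latter is a useful model for wording, not a contradiction.
- **That the design puts the 16-week route out of reach for those who stop treatment early.** They attend the EDV and "then go to the following scheduled visits exactly as subjects who are still on-treatment, for a total of 3 months", but neither document says when the 3 months start. Protocol 8.5.2 also asks participants with treatment-emergent ADA to return 3 months after the first positive, and again 3 months later if still positive. Such samples could span 16 weeks.
- **That the 16-week route cannot be met at the primary analysis.** SAP 1.1 times that analysis by the point when all participants still in the study have completed Visit 10. Earlier participants may have later samples by then, and the cut-off rules sit in a separate charter.

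**Conclusion.** The point holds as a small but real derivation error. Followed as written, the SAP counts participants never tested after dosing as TE-ADA non-events, or as only baseline positive and TE-ADA negative, and can report pre-existing ADA as treatment-induced when the one scheduled baseline is missing. The definition of persistence needs one clarifying term.

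The positive and missing counts behind the shifts of a few percentage points are assumptions. The shifts are small beside the sampling uncertainty of an arm of 27, and the two biases partly offset if both occur. No hypothesis test depends on this endpoint. It is still worth changing, because the correct derivation is available from the same data and the present one reports untested participants as results.

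**What to change.** In SAP 4.2.5.4:

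1. Drop the missing-as-negative rule for the TE-ADA categories.
2. Compute TE-ADA, treatment-induced and treatment-boosted incidence in participants with a baseline and at least one post-baseline ADA result.
3. Show the number not evaluable per arm.
4. Put participants with a post-baseline positive but no baseline on a separate line, so that no positive is lost.
5. Define the last post-baseline assessment as the last available result, as SAP 3.3.3.5 does for ECG.

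A sentence in 4.2.6.1 on participants who lack a baseline or any post-baseline sample would align the two sections.

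The cost is SAP wording and a change in derivation. Denominators become slightly smaller, and positives without a baseline leave the TE-ADA count for their own line.

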## **4.2.6 Safety endpoints**

### **4.2.6.1 Adverse events**

After having assigned the AEs to the corresponding study phase as described in section 3.3.3.1, the AEs will be summarized for each treatment group. The AEs tables will be based on the safety analysis set. Summary tables will include AEs in the on-treatment phase as described in section 3.1.3.

Summary tables are listed below.

An overview table containing:

- Number and percentage of subjects with any AEs
- Number and percentage of subjects with any AEs with outcome of death
- Number and percentage of subjects with any SAEs
- Number and percentage of subjects with any AEs leading to discontinuation / interruption / reduction of IP
- Number and percentage of subjects with any AEs leading to withdrawal from study

An overview table by ADA category containing:

- Number and percentage of subjects with any AEs
- Number and percentage of subjects with any AEs with outcome of death
- Number and percentage of subjects with any SAEs
- Number and percentage of subjects with any AEs leading to discontinuation of IP

The following summary tables will be presented by SOC and PT:

- The number and percentage of subjects with any AEs
- The number of AEs
- The number and percentage of subjects with AEs with outcome of death
- The number and percentage of subjects with SAEs
- The number of SAEs
- The number and percentage of subjects with AEs leading to discontinuation.

The following summary tables will be presented by PT:

- The number and percentage of subjects with most common AEs (frequency of >5%)
- The number and percentage of subjects with any AEs by maximum reported intensity
- The number and percentage of subjects with any AEs and investigator's causality assessment. If a subject has multiple events in the same PT, the event with the strongest relationship will be counted.

Where number of subjects with AEs are summarized by SOC and/or PT, subjects with multiple events in the same SOC/PT are counted only once in that SOC/PT. Subjects with events in more than 1 SOC/PT are counted once in each of those SOC/PTs.

Additionally, the following tables will be presented:

- the number of subjects with serious adverse events, by seriousness criteria
- number and percentage of subjects with non-serious AEs occurring with a frequency > 5.0% in any treatment group for each SOC and PT. This table will be produced as a separate pdf output to meet clinical trial transparency requirements and not for inclusion in the CSR. It will be delivered at the same time as the CSR outputs.
- the number of subjects with injection site reactions by HLT and PT
- the number of subjects with bleedings by SMQ and PT

A list of key subject information for subjects with AEs with outcome of death, subjects with SAEs, and subjects with AEs leading to discontinuation of IP will be provided. The durations reported in these tables, will be derived only for fully completed dates as below:

- Time from first dose of IP to AE (in days) will be calculated as the AE start date minus date of first dose of IP +1.
- Time from first dose to death (in days) will be calculated as the date of death minus date of first dose of IP +1.
- The same approach will be used for deriving time from start of treatment to AE becoming serious or discontinuation.
- Time from last dose prior to AE start and last dose prior to death (in days) will be calculated as the date of death minus the date of last dose prior to AE/death +1.

All the AEs will also be listed for all subjects included in the safety analysis set. AEs among ADA positive and ADA negative subjects will also be listed. A subject is considered ADA

negative if collected samples are tested negative at all timepoints, including baseline and post-baseline. Regarding ADA positive categories in section 4.2.5.4 are included.

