| Anti-drug Antibodies             | There is a potential risk for antibody formation. Emergence of ADA has been observed in a proportion of clinical study participants after repeated oligonucleotide treatment, leading to change in PK profile. To date, no apparent association of ADA with loss of efficacy or safety findings have been observed.   | Assessment of ADAs and monitoring for immunogenicity effects (including hypersensitivity reactions and ADA effect on PK/PD). Guidance on the definition of an anaphylactic reaction and the action plan that needs to be followed with regards to ADA sampling is presented in Appendix G . |
| Injection Site Reactions         | As with any exogenous substance, injection site reactions may occur as a response to the SC injection of AZD8233. Possible risks associated with SC administration are redness, swelling, pain, induration, and sometimes infection at the administration site. Although observed for some ASOs, injection site reactions are not generally a clinical problem for newer generation ASOs. | Monitoring for injection site reactions   |
| Complement Activation            | This is a known class effect of oligonucleotides and appears to be directly plasma concentration ( $C_{max}$ ) driven. Monkeys are considered more sensitive to complement activation than humans ( Crooke ST et al 2016 ). No indication of complement activation induced by AZD8233 have been observed in toxicology studies.   | Assessment of complement activation around $C_{max}$ (C3a, C5a, Bb)   |
| Increased Bleeding Risk          | Increases in aPTT, in the absence of clinical or pathological sequelae, have been observed with ASOs ( Burel S et al 2013 , Henry SP et al 1997 ). Mechanistically, interaction of ASOs with the intrinsic tenase complex and thrombin results in a selective inhibition of the intrinsic clotting  | Assessment of aPTT and PT   |

| Potential Risk of Clinical Significance | Rationale for Risk   | Mitigation Strategy (refer to IB Section 5.5 for further detail)  |
|---|--|---|

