## **3.3.3 Safety endpoint**

### **3.3.3.1 Adverse events**

An adverse event is the development of any untoward medical occurrence in a subject or clinical study subject administered a medicinal product and which does not necessarily have a causal relationship with this treatment. An AE can therefore be any unfavourable and unintended sign (e.g., an abnormal laboratory finding), symptom (e.g., nausea, chest pain), or disease temporally associated with the use of a medicinal product, whether or not considered related to the medicinal product. The term AE is used to include both serious and non-serious AEs and can include a deterioration of a pre-existing medical occurrence. An AE may occur at any time, including run-in or washout periods, even if no study treatment has been administered. SAEs will be collected from time of signature of informed consent, throughout the treatment period

and including the follow-up period. All non-serious AEs will be recorded from time of first dose of IP, throughout the treatment period and including the follow-up period. Adverse events (AEs) will be coded with MedDRA version 23.0 or higher. For any additional details on AE reporting please refer to the study protocol.

After start and end date imputation as per section 3.1.1 the AEs are assigned to the study phases described in section 3.1.3, based on the AE start date and time as follows:

If both the start date and start time of an AE are known, then:

- If the AE start datetime is before the first dose of IP datetime, then the AE is assigned to the pre-treatment phase.
- If the AE start datetime is on or after the first dose of IP datetime, then the AE is assigned to the on-treatment phase,

If only the start date of an AE is known, and the start time of the AE is unknown, then:

- If the AE start date is before the first dose of IP date, then the AE is assigned to the pre-treatment phase,
- If the AE start date is on or after the first dose of IP date then the AE is assigned to the on-treatment phase,

If the start date of an AE is completely missing, the AE is assigned as follow:

- If the AE end date is known and is before the first dose of IP date, then the AE is assigned to the pre-treatment phase,
- If the AE end date is completely missing or if the AE end date is on or after the first dose of IP date no assignment can be done.

All the AE in the on-treatment phase are considered TEAEs.

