All immunogenicity parameters will also be reported in a listing for the full analysis set. Days from previous dose of IP will be calculated as the ADA date minus date of previous dose +1. Days from previous dose of IP for ADA measured during pre-treatment period will be set to missing. Listings of all subjects excluded from the ADA analysis set will also be provided. The listing will be based on all enrolled subjects.

The following figures will be also provided for complete analysis only:

A spaghetti plot figure with individual plotted ADA-titres over time in subjects with any positive ADA-response, one graph per treatment group (including placebo).

A boxplot exploring ADA positive vs ADA negatives impact on PK concentrations over time, percent change on PCSK9 and percent change on LDL over time, one graph per treatment group (including placebo).

A figure showing the percentage of subjects with positive ADA results over time.

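### The AE overview by ADA category has no timing rule, so AEs that began before a participant's first positive ADA sample are shown under ADA-positive

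*SAP*

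**What the plan says.** **The table.** SAP 4.2.6.1 introduces it with "An overview table by ADA category containing" and lists four rows: participants with any AE, with a fatal AE, with an SAE, and with an AE leading to discontinuation of IP. It does not name the ADA categories to be used, and it does not relate an AE to the date of any ADA sample.

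**The AE window.** The same section states: "Summary tables will include AEs in the on-treatment phase as described in section 3.1.3". SAP 3.3.3.1 sets the start: "If the AE start datetime is on or after the first dose of IP datetime, then the AE is assigned to the on-treatment phase". SAP Table 5 runs the phase "to the end of study date", which is Day 169 for a participant who completes.

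**The ADA categories.** SAP 4.2.5.4 defines them per participant, with post-baseline meaning that same on-treatment phase. One category is "ADA positive at baseline and/or post-baseline (ADA prevalence". Another reads: "Treatment-induced ADA positive is defined as ADA negative at baseline and post-baseline ADA positive". The date of first positivity plays no part. Missing ADA results count as negative (SAP 4.2.5.4). A participant is ADA-negative when every sample actually collected was negative (SAP 4.2.6.1). One ADA assessment, which may be the baseline one, is enough to enter the ADA analysis set (SAP Table 2).

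**The figures.** SAP 4.2.5.4 also plans "A boxplot exploring ADA positive vs ADA negatives impact on PK concentrations over time", with the same for PCSK9 and LDL-C. It does not say whether status is taken per participant or per visit.

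**The purpose.** Protocol Table 2 gives as mitigation for the antibody risk: "Assessment of ADAs and monitoring for immunogenicity effects (including hypersensitivity reactions and ADA effect on PK/PD".

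**The concern.** An AE can be linked to an antibody only if the antibody was there when the AE began. Classifying a participant once, over the whole study, and then counting all AEs from Day 1 ignores that order. Early AEs of later converters are credited to ADA-positive, so a real excess after seroconversion is mixed with time before it.

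There is also an asymmetry. A participant must stay long enough to give a positive sample, so someone who leaves early has less chance of being classed ADA-positive.

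Immunogenicity is a secondary objective, and this is the only planned summary table that sets AEs against ADA status. A reader of the study report will look there for a safety signal from antibodies.

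**Working it through.** The plan states no figure for this table, so there is none to reproduce.

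**1. The rules applied to one case.** Take an AE on Day 8 in a participant whose first positive sample is on Day 113. The AE falls in the on-treatment phase, so it is counted. The participant was negative at baseline and positive later, so is treatment-induced ADA-positive. The AE is shown under ADA-positive although the samples on Days 8, 29, 57 and 85 were all negative.

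**2. Share of the AE window before detection.** ADA sampling days (SAP Table 1, footnote j) are Days 1, 8, 29, 57, 85, 113 and 141, plus the final visit (Day 169) or EDV. For a completer the window is 169 days, and the share is (day of first positive − 1)/169.

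- Day 57: 56/169 = 33%
- Day 85: 84/169 = 50%
- Day 113: 112/169 = 66%

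The last dose is on Day 57, so a participant first positive on Day 85 received all four doses before detection.

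**3. Effect on a real link.** The documents give no AE rate. Assume 1 AE per 24 weeks, doubling after detection. Expected AEs are then 2 − share, and the percentage with any AE is 1 − exp(−(2 − share)). Without any effect it is 1 − exp(−1) = 63%.

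| First positive | Expected AEs | Any AE | Ratio to 63% |
|---|---|---|---|
| Day 57 | 1.67 | 81% | 1.28 |
| Day 85 | 1.50 | 78% | 1.23 |
| Day 113 | 1.34 | 74% | 1.17 |
| Doubling from Day 1 | 2.00 | 86% | 1.37 |

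**4. No real link.** The documents give no ADA incidence, onset time or drop-out timing. A simulation of 400,000 participants per scenario used these assumptions:

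- ADA in 20% or 40% of participants, with mean onset on Day 40 or 85
- 1 AE per 24 weeks, unrelated to ADA
- drop-out of 0%, 10% or 26%, spread evenly over time; 26% is 1 − 80/108, from the planned numbers in SAP 1.3
- an EDV sample always taken

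Results under the ever-positive rule:

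- 30–48% of AEs in ADA-positive participants came before their first positive sample.
- 22–40% of ADA-positive participants with any AE had only such earlier AEs.
- With full follow-up, any-AE was about 63% in both groups.
- With 10% drop-out, ADA-positive was 1.4–2.3 points higher; with 26%, 2.9–5.9 points higher.
- With 26% drop-out, 27–30% of ADA-negatives were drop-outs, against 17–22% of ADA-positives.

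**5. The discontinuation row.** Protocol section 8 ties the EDV to stopping treatment before Visit 8, the Day 57 dose. AEs leading to discontinuation of IP therefore fall essentially within Days 1–57. For anyone first positive after Day 57, this row cannot reflect a detected antibody. A participant who stops after the Day 8 dose has the EDV at about Day 22. Three further months (91 days) reach about Day 113, so the Day 141 and Day 169 samples would usually be missed.

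**The case against.** The strongest reply is that this is an untested descriptive overview and the order of events can be recovered elsewhere. AEs are listed by ADA status, and study days are derived for both AEs and ADA samples. Titres are plotted individually, and the key-information lists for deaths, SAEs and discontinuations give time from first dose. For rare events in about 108 participants, case review can establish which came first. This stands as partial mitigation, but none of these outputs is specified to order AEs against the first positive sample, and the summary table remains as defined.

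Second, stopping treatment is not leaving the study. Protocol 7.1 asks for an EDV and continued visits for three months, and the EDV includes an ADA sample. A participant with short exposure and no antibody is correctly negative. This also stands, so the tilt is modest. With 108/4 = 27 per arm and an assumed 20–40% ADA incidence, an arm has roughly 5–11 ADA-positive participants. One participant then moves a cell by about 9–20 points, more than the simulated gap of at most 5.9.

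Third, splitting the table into person-time rates would bring its own bias. Time after detection is later and often off dosing, so dose-related AEs could make ADA look protective. A split at the first positive sample also does nothing for treatment-boosted participants, who are positive at baseline. Both points stand and shape the fix.

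A reader might infer that a true doubling would appear in the table as a ratio of 1.67, 1.50 or 1.34. Those are event-rate ratios (2 − share). The table gives percentages of participants, each counted once, so the figures would be approached only in rare rows.

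**Conclusion.** The point holds as a gap in one descriptive safety table. The SAP counts AEs over the whole study under ever-positive ADA status and orders nothing against the first positive sample. The 33%, 50% and 66% shares follow from the visit schedule for a completer. The attenuation and drop-out figures rest on assumed AE rates, ADA incidence, onset and drop-out.

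Three stronger readings are not supported.

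- A reader might infer that the rule manufactures an ADA effect by itself. With full follow-up and no true link it creates no difference between groups; it blurs timing and dilutes a real effect.
- A reader might infer that the discontinuation row can reverse. The documents give no figures from which to show that; a modest lean towards ADA-negative is as far as the schedule goes.
- A reader might infer that the boxplots mix visits before and after seroconversion. SAP 4.2.5.4 does not say how they classify, so the defect there is a missing rule.

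The primary LDL-C analysis is unaffected.

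**What to change.** Keep the planned table and state which ADA categories it uses. Then:

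- **Add timing rows for TE-ADA-positive participants.** Give the number and percentage with AEs, with SAEs, and with AEs leading to discontinuation of IP that start before, versus on or after, the first sample meeting the TE-ADA definition. That is the first positive sample if treatment-induced, and the first sample with a ≥4-fold titre rise if treatment-boosted.
- **Add a not-evaluable column** for participants with no post-baseline ADA result, instead of counting them as negative. This also settles the denominator, since AE tables use the safety analysis set while ADA categories exist only in the ADA analysis set.
- **State the boxplot rule:** classify each visit by ADA status at or before that visit.
- **Say how AEs with partial start dates are placed,** because SAP 3.3.3.1 leaves their study day missing.

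The cost is a paragraph in the SAP and a small programming change; no new data are needed. The SAP should state three limits. Onset is known only to lie between two samples. Cells will be small. Time after first detection is later and often follows the last dose on Day 57, so the before and after counts are descriptive and must not be read as a causal rate comparison.
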